9.1.1.4 Assessment of effectiveness

Asthma control status:

Asthma control status will be assessed based on the “Asthma prevention and management guideline” [[! "#\\$%"&%](#)

9.1.1.4: 1 Asthma control status Table

Patients control status	Well-controlled	Insufficiently-controlled	Poorly-controlled
	Meet all the criteria	Meet 1 or 2 criteria	Meet all of 3 Criteria
Asthma symptoms (in the daytime or at night)	None	Once or more a week	Once or more a week
Use of reliever	None	Once or more a week	Once or more a week
Limitation of activities, including exercise	None	Restricted	Restricted

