### **5.4 OTHER VARIABLES**

#### **Demographic data and baseline characteristics:**

- Sex: male, female
- Age [years]  
Age [years] = Actual age based on the first administration of Spriva Respimat  
[REDACTED]
- Height [cm]
- Weight [kg]  
[REDACTED]
- Body mass index (BMI) [ $\text{kg}/\text{m}^2$ ]  
BMI [ $\text{kg}/\text{m}^2$ ] = weight [kg] / (height [m])  
[REDACTED]
- [REDACTED]
- Smoking status: Never smoked, Ex-smoker, Current smoker, Unknown
- Pack-Years  
[REDACTED]
- [REDACTED]
- Indication for use: Bronchial asthma, Other
- Asthma Severity: Severe persistent, Moderate persistent, Mild persistent, Intermittent, Unknown

- Duration of asthma [years]  
Duration of asthma = [First administration of Spiriva Respimat – Date of indication of asthma + 1 (if negative value, then 1)] / 365.25: Day of indication is 1.  
[REDACTED]

- Number of hospital admission due to asthma in the past year (Statistics and frequency)
- Number of urgent visit to physician due to asthma in the past year (Statistics and frequency)
- Medical history: Yes, No, Unknown  
[REDACTED]

- Concomitant diagnosis: Yes, No, Unknown  
[REDACTED]

- Previous Medication: Yes, No, Unknown  
Note: Previous medications are existing drugs, drugs which administered before initiation of the new anti-asthmatic drug, drugs of unknown starting date.  
[REDACTED]

- Concomitant Medication during treatment of Spiriva Respimat: Yes, No, Unknown
  - Note: Treated during treatment period of Spiriva Respimat regardless of the start and end date of the medication (except for the case that the end date of the medication and the start date of Spiriva Respimat are the same)SABA: Yes, No, Unknown

- Concomitant therapy: Yes, No, Unknown
- Pulmonary Function Test

- Asthma control status at baseline (see the CTP Section 9.1.1.4): Well-controlled, Insufficiently-controlled, Poorly-controlled, Unknown

- Asthma symptoms (in the daytime or at night): Yes, No, Unknown
- Use of reliever: Yes, No
- Limitation of activities, including exercise: Yes, No, Unknown
- PEFR (mean of the 7 days before each visit) [L/min]
- Pregnancy test: Yes, No, Unknown
- ACQ 6 score at baseline (each score and mean of 6 questions)
- Contraindication to Spiriva Respimat: Yes, No

[REDACTED]

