## **7.5 SECONDARY ENDPOINTS**

Effectiveness at each visit in each patient is determined based on the change of asthma control status from baseline. See the assessment table for effectiveness and the CTP Section 9.1.1.4. And it will be performed as well as [Section 5.4](#). Calculate worse odds ratio in each patient characteristic (demographic and existing treatment factor).

Table 7.5: 1 Assessment table for effectiveness

	Well controlled at baseline	Insufficiently-controlled at baseline	Poorly-controlled at baseline
Well controlled after administration	Improvement	Improvement	Improvement
Insufficiently-controlled after administration	Worse	Worse	Improvement
Poorly-controlled after administration	Worse	Worse	Worse

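### The odds ratios of 'worse' are planned without adjustment for baseline asthma control, although the threshold for 'worse' depends on it, so they may partly reflect baseline mix

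*SAP*

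**What the plan says.** SAP 7.5 defines the outcome by visit: "Effectiveness at each visit in each patient is determined based on the change of asthma control status from baseline". Table 7.5: 1 then sorts every pair of baseline and later status into one of two classes, with no class for unchanged:

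- "Well controlled after administration": Improvement from all three baseline levels.
- "Insufficiently-controlled after administration": Worse if the patient started well or insufficiently controlled, Improvement if poorly controlled.
- "Poorly-controlled after administration": Worse from all three baseline levels.

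The same section adds: "Calculate worse odds ratio in each patient characteristic (demographic and existing treatment factor". It names no model, covariate or stratum. The only odds-ratio method in the visible SAP is in 7.8.1, where logistic regression is named for the ADR subgroups, without covariates.

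SAP 5.4 lists among the baseline characteristics: "Asthma control status at baseline (see the CTP Section 9.1.1.4): Well-controlled, Insufficiently-controlled, Poorly-controlled, Unknown". The variable is therefore recorded, but nothing visible uses it to adjust the other odds ratios. The checklist in Protocol Annex 2 answers No on stratified analyses (10.4), adjustment for confounding (10.5) and effect modification (10.6). SAP section 4 reports no change from the protocol's methods. Protocol 9.7 calls the analyses descriptive.

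**The concern.** The same end state is scored in opposite ways depending only on where the patient began: ending insufficiently controlled is a success from poor and a failure from well. The probability of 'worse' will therefore generally differ by baseline level, even if a characteristic has no influence at all.

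Starting levels can also differ between subgroups. Protocol 9.2.2.1 selects on severity, classified by present treatment, and requires no particular level of control. Recorded characteristics such as past-year admissions, urgent visits and ICS dose category plausibly go with baseline control, although the documents give no data on this.

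If they do, a crude odds ratio mixes two things: any difference between patients who started alike, and the difference in starting mix. A reader of the report, or of the re-examination file, could take the second for the first and treat a marker of baseline control as a predictor of response.

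**Working it through.** **1. Plan's own figure.** The documents state no expected odds ratio, transition rate or baseline mix, so there is nothing to reproduce. All rates and mixes below are assumptions.

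**2. Threshold by baseline level, from Table 7.5: 1.**

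- Well at baseline: P(worse) = 1 − P(well after); 2 of 3 end states are Worse.
- Insufficient at baseline: P(worse) = 1 − P(well after); 2 of 3.
- Poor at baseline: P(worse) = P(poor after); 1 of 3.

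**3. Assumed end states (well/insufficient/poor), identical in both groups.**

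- From well, 70/25/5%: P(worse) = 1 − 0.70 = 0.30.
- From insufficient, 35/50/15%: P(worse) = 1 − 0.35 = 0.65.
- From poor, 20/40/40%: P(worse) = 0.40.

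Because the rates are the same in both groups, the odds ratio within each baseline level is 1.00. Any departure in the crude odds ratio comes from starting mix.

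**4. Crude odds ratio.** For each group, p = Σ (share at baseline level × P(worse) at that level); OR = [pA/(1 − pA)] / [pB/(1 − pB)].

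Moderately different mixes (well/insufficient/poor), A 10/30/60 and B 30/50/20:

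- pA = 0.10×0.30 + 0.30×0.65 + 0.60×0.40 = 0.465
- pB = 0.30×0.30 + 0.50×0.65 + 0.20×0.40 = 0.495
- OR = (0.465/0.535) / (0.495/0.505) = 0.89

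Extreme mixes, A 0/20/80 and B 0/80/20:

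- pA = 0.20×0.65 + 0.80×0.40 = 0.45
- pB = 0.80×0.65 + 0.20×0.40 = 0.60
- OR = (0.45/0.55) / (0.60/0.40) = 0.55

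**5. How far this depends on the assumed rates.** Mixes held at 5/35/60 versus 20/60/20, with five other sets of rates:

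| P(worse) from well / insufficient / poor | pA | pB | Crude OR |
|---|---|---|---|
| 0.70 / 0.70 / 0.20 | 0.400 | 0.600 | 0.44 |
| 0.30 / 0.65 / 0.40 | 0.4825 | 0.530 | 0.83 |
| 0.15 / 0.80 / 0.60 | 0.6475 | 0.630 | 1.08 |
| 0.15 / 0.40 / 0.20 | 0.2675 | 0.310 | 0.81 |
| 0.40 / 0.40 / 0.40 | 0.400 | 0.400 | 1.00 |

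The group with more poorly controlled patients can look better, worse or the same. Across all unequal mixes tried with these five sets, the crude odds ratio ran from 0.44 to 1.50; with equal mixes it was 1.00. A wider draw of 2,213 assumed sets of rates, ordered so that a better start gives a better end, with mixes 10/50/40 versus 10/70/20, gave a median of 0.89 and a 5th to 95th percentile range of 0.70 to 1.11.

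**6. After conditioning on baseline level.** The odds ratio is 1.00 in every case, by construction.

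**The case against.** The case for leaving the plan alone is reasonable. The analysis is descriptive and secondary to safety. A crude odds ratio is a legitimate account of who ends up classed as worse, and no passage says that characteristics will be reported as predictors. Baseline status is not absent: it defines the outcome, and since it is listed in SAP 5.4 it may get an odds ratio of its own. SAP 6.4, which defines the subgroups, is not visible, and parts of 5.4 are blacked out.

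Part of this stands. The consequence is limited to misreading of descriptive output, and it would be too strong to say that baseline status is ignored. But giving baseline control its own row leaves every other odds ratio unadjusted.

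Two stronger readings are tempting, and the documents support neither.

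- *A reader might infer that the floor of the scale bars the sickest patients from worsening.* Table 7.5: 1 classes a patient who starts and stays poorly controlled as Worse, so no baseline level has a probability of 'worse' fixed at 0 or 1. The floor would bite only if 'worse' meant a strict drop in level. In the first example P(worse) would then be 0.30, 0.15 and 0 from well, insufficient and poor, giving 0.075 versus 0.165 and an odds ratio of 0.41. The SAP does not use that definition.
- *A reader might infer that the odds ratios mainly show how the groups started.* Nothing establishes this. The shift depends on rates and mixes that the documents do not give, and it may be small or nil.

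**Conclusion.** The point holds in a limited form. SAP 7.5 shows no adjustment for baseline control, while its own table makes the threshold for 'worse' depend on baseline control. Crude odds ratios may therefore partly reflect baseline mix wherever a characteristic is associated with baseline control and the chance of 'worse' differs between levels. If either condition fails, there is no distortion.

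The size cannot be derived from the documents. The worked values of 0.89 and 0.55 illustrate moderate and extreme differences in mix under assumed rates; other assumed rates move the result to either side of 1.00. It is worth correcting because the remedy is nearly free, not because a large bias has been shown.

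**What to change.** In SAP 7.5:

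- State that each odds ratio of 'worse' is estimated by logistic regression with the characteristic and baseline asthma control status (well, insufficiently, poorly controlled) as a three-level factor. The exception is baseline control status itself, which is reported unadjusted.
- Report the adjusted odds ratio beside the crude one.
- Show the baseline control mix for each category of each characteristic. This matters because crude and adjusted odds ratios can differ somewhat even without confounding, so the gap between them should be read with the mix in view.

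The cost is SAP wording, two extra model parameters and one added block in the table. No new data are needed, since SAP 5.4 already lists the variable. No classifiable patient is lost, because a patient whose baseline control is unknown cannot be placed in Table 7.5: 1 in the first place. If a baseline level has too few patients for a stable fit, the counts of 'worse' by baseline level can be shown instead.

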9.1.1.2 Secondary outcome

- Change from baseline in asthma control status at Week 52

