9.5 STUDY SIZE

It is planned to enroll 360 patients with severe persistent asthma: 360 patients will initiate the Spiriva Respimat treatment, assuming 60 patients out of 360 patients will be dropped out without any data being collected.

The planned number of patients is not driven by a formal sample size calculation but is primarily based on the availability of patients eligible for Spiriva Respimat treatment.

300 patients will be registered for this study. The frequently observed ADR ($\geq 1.0\%$) in special use surveillance for Spiriva Respimat in patients with COPD was Coughing (1.2%). The frequently observed ADRs ($\geq 1.0\%$) in the clinical trial in Japanese patients with asthma were asthma (1.8%), dysphonia (1.8%) and dry mouth (1.8%). In the number of cases to be surveyed, it is evaluated if there is no possibility that the trend of incidence of these main adverse events would be largely increased compared to that of COPD patients.

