9.7 DATA ANALYSIS

This is a non-interventional, observational study to collect new real-world data (i.e., data under routine medical practice) on safety and effectiveness of Spiriva Respimat treatment in patients. Analyses are descriptive in nature. Due to the nature of the observational study, no confirmatory statistical testing is foreseen in this study.

Per local regulation, any patient who meets one of the following criteria is treated as ineligible for all analyses:

- No safety observation was documented after registration
- No required registration procedure was followed
- No valid site contract was available

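### SAP 7.5 relates three-level asthma control to patient characteristics only through a two-way 'worse' odds ratio whose cut moves with baseline status, and states no adjustment for baseline

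*SAP*

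**What the plan says.** Protocol 9.1.1.2 gives the secondary outcome as "Change from baseline in asthma control status at Week 52". Protocol 9.1.1.4 defines the scale: "Asthma control status will be assessed based on the" cited guideline, with three ordered levels (well, insufficiently and poorly controlled).

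SAP 7.5 then states: "Effectiveness at each visit in each patient is determined based on the change of asthma control status from baseline". Its Table 7.5:1 assigns each of the nine baseline-by-follow-up cells one of two labels:

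| Follow-up | Well at baseline | Insufficient at baseline | Poor at baseline |
|---|---|---|---|
| Well | Improvement | Improvement | Improvement |
| Insufficient | Worse | Worse | Improvement |
| Poor | Worse | Worse | Worse |

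The analysis by characteristic is one instruction: "Calculate worse odds ratio in each patient characteristic (demographic and existing treatment factor". Section 7.5 names no model, confidence interval or baseline covariate for it. Logistic regression with a 95% interval is specified in SAP 7.8.1, for the adverse-reaction subgroups.

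On the aims, Protocol 9.7 says "no confirmatory statistical testing is foreseen in this study", and Protocol 9.5 says "The planned number of patients is not driven by a formal sample size calculation".

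**The concern.** Reading Table 7.5:1 down its columns shows two features.

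- **Merged levels.** Poor-to-well counts the same as poor-to-insufficient, insufficient-to-poor the same as insufficient-to-insufficient, and well-to-poor the same as well-to-insufficient. The odds ratio cannot show a characteristic that is linked to the degree of response, and it is usually less precise than the recorded data allow.
- **A cut that moves with baseline.** The split is well versus not well in the first two columns and not poor versus poor in the third. The probability of being called worse therefore depends on the starting level. Without adjustment, a characteristic that goes with a different baseline mix can show an odds ratio away from 1 when it has no association with outcome at any given baseline level.

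At stake is the description of which patients do better or worse on this outcome. At most about 300 patients are expected. Control status is recorded only if available (Protocol 9.3 and Annex 3), so fewer may have a rating.

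**Working it through.** **The plan's own figure.** The only figure to reproduce is enrolment (Protocol 9.5): 360 − 60 = 300. No power, interval width or precision is stated for the 'worse' odds ratio.

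**Inputs.** N = 300 comes from the protocol and is an upper bound. Everything else is assumed, because the documents give no distribution of control status: a characteristic present in f = 0.5 of patients, and five sets of baseline shares and follow-up probabilities (W/I/P = well/insufficient/poor).

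**Formula.** The information on a common log odds ratio within a baseline level of size n is V = n·f·(1−f)·(1 − Σp³)/3, where p are the follow-up probabilities. With two categories this becomes n·f·(1−f)·p·(1−p). Sum V over baseline levels; SE = 1/√V. Both analyses are stratified by baseline, so the difference is due to the cut alone.

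**One case in full (row 2 of the table below).**

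| Baseline | n | Follow-up W/I/P | P(worse) | V ordinal | V two-way |
|---|---|---|---|---|---|
| Well | 30 | .75/.20/.05 | .25 | 7.5×.570/3 = 1.43 | 7.5×.1875 = 1.41 |
| Insufficient | 150 | .40/.50/.10 | .60 | 37.5×.810/3 = 10.13 | 37.5×.24 = 9.00 |
| Poor | 120 | .20/.50/.30 | .30 | 30×.840/3 = 8.40 | 30×.21 = 6.30 |
| Sum | 300 | | | 19.95 | 16.71 |

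SE = 1/√16.71 = 0.245 (two-way) against 1/√19.95 = 0.224 (ordinal), a ratio of 1.09.

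**All five cases.** The last column is the share of patients coded Worse whose status did not change.

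| Baseline W/I/P | Follow-up W/I/P from well; insufficient; poor | SE two-way | SE ordinal | Ratio | Unchanged among Worse |
|---|---|---|---|---|---|
| thirds | thirds throughout | 0.245 | 0.212 | 1.15 | 40% |
| .10/.50/.40 | .75/.20/.05; .40/.50/.10; .20/.50/.30 | 0.245 | 0.224 | 1.09 | 83% |
| .10/.50/.40 | .85/.13/.02; .20/.70/.10; .08/.37/.55 | 0.264 | 0.243 | 1.08 | 90% |
| .05/.45/.50 | .90/.09/.01; .65/.32/.03; .40/.50/.10 | 0.296 | 0.234 | 1.27 | 91% |
| 0/1/0 | insufficient only: .60/.37/.03 | 0.236 | 0.234 | 1.01 | 92% |

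The 95% interval multiplies and divides the odds ratio by 1.59 to 1.79 (two-way) or 1.52 to 1.61 (ordinal). With N = 200 or f = 0.2 both standard errors rise and the ratios stay the same.

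**Simulation check.** In one assumed setting (true odds ratio 1.8, 300 runs, both models baseline-adjusted), the empirical SD of the log odds ratio was 0.260 two-way and 0.238 ordinal. The interval excluded 1 in 62% and 71% of runs. Monte Carlo error is about √(0.62×0.38/300) = 0.028, or 3 points per share.

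**Baseline mix.** Take the row 2 probabilities and a characteristic with no effect within any baseline level. Without it, let baseline be .10/.50/.40; with it, .10/.30/.60.

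- P(worse) without: .10×.25 + .50×.60 + .40×.30 = .445.
- P(worse) with: .10×.25 + .30×.60 + .60×.30 = .385.
- Unadjusted odds ratio: (.385/.615)/(.445/.555) = 0.78. Within each baseline level it is 1.
- Poorly controlled at follow-up without: .10×.05 + .50×.10 + .40×.30 = .175. With: .10×.05 + .30×.10 + .60×.30 = .215.

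The group that ends with more poor control thus appears to have lower odds of being worse.

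**The case against.** The strongest reply is that the plan misses no target of its own. The study is descriptive, has no primary effectiveness outcome and no formal sample size, and sets no precision for this odds ratio. The chance that an interval excludes 1 is a power argument for a test that nobody plans. That stands, and it makes this an improvement rather than an error.

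The second reply is that the comparison favours the ordinal model by assuming proportional odds, which nothing in the documents supports. This also stands. In one further assumed setting (N = 300, baseline 10/50/40%, follow-up .75/.20/.05; .45/.47/.08; .20/.45/.35, odds ratio 1.8, 400 runs), the interval excluded 1 in 70.5% (ordinal) against 68.5% (two-way) under proportional odds. When the characteristic acted only at the SAP's own cut for each baseline level, the result reversed: 47.8% against 68.0%, with the ordinal odds ratio at 1.56 instead of 1.80. There the two models estimate different quantities. Neither reply removes the baseline-mix problem, which needs no proportionality assumption.

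Three stronger readings are tempting but not supported:

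- **A firm loss.** Some plausible mixes give 15% to 22% lower variance and 4 to 13 more points of intervals excluding 1. The wider set above shows that this range is too narrow, and the documents cannot say which case applies.
- **The third level is lost from the report.** SAP 7 keeps every category in frequency tables and lists individual effectiveness values. The loss concerns the odds ratio.
- **No rationale or other analysis exists.** SAP 6.4 and 7.6 and Protocol 9.1.1.3 are not visible in the public copy, so absence cannot be inferred.

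**Conclusion.** The point holds as an efficiency and specification weakness in the visible text of SAP 7.5. The 'worse' odds ratio merges two follow-up levels in every baseline column, uses a cut that shifts with baseline, and has no stated baseline adjustment.

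The standard-error penalty from the cut is about 1% to 27% under the five assumed sets of rates and a common odds ratio. It is smallest when everyone starts insufficiently controlled and few end poor, and largest with strong response among patients who start poor. Without proportional odds the advantage can disappear or reverse. The distortion from baseline mix is a matter of validity; its size depends on how far the mix differs between groups (0.78 instead of 1 in the example).

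The label is a related problem in the same table. Insufficient-to-insufficient and poor-to-poor are coded Worse, and such patients make up 40% to 92% of Worse in the assumed cases. Greater precision would not cure that.

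**What to change.** Revise SAP 7.5 as follows.

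1. For each patient characteristic, estimate a common odds ratio with 95% CI for a worse level of asthma control from a proportional-odds model with baseline control status as covariate. Do this at Week 52, and also at Weeks 4 and 12 because 7.5 assesses each visit.
2. Present the 3x3 baseline-by-visit table for each level of the characteristic.
3. Keep the binary odds ratio as a supportive display, adjusted for baseline control status. Label it 'not improved', or add an explicit 'unchanged' category. Under the first option, add a footnote that well-to-well is counted as Improvement.

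The cost is SAP wording and one standard SAS model per characteristic and visit, on data already collected. The downside is reliance on roughly proportional odds, which the 3x3 tables and the retained binary odds ratio let readers check. If only one change is made, the baseline covariate matters most, because it removes the baseline-mix distortion whichever outcome scale is used.

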## **7.7 EXTENT OF EXPOSURE**

Only descriptive statistics are planned for this section of the report.

## **7.8 SAFETY ANALYSIS**

All safety analyses will be performed on the safety set.

### **7.8.1 Adverse events**

Unless otherwise specified, the analyses of adverse events will be descriptive in nature. All analyses of AEs will be based on the number of patients with AEs and NOT on the number of AEs.

Furthermore, for analysis of AE attributes such as duration, severity, etc. multiple AE occurrence data on the CRF, will be collapsed into AE episodes provided that all of the following applies:

- The same MedDRA lowest level term was reported for the occurrences
- The occurrences were time-overlapping or time-adjacent (time-adjacency of 2 occurrences is given if the second occurrence started on the same day or on the day after the end of the first occurrence)
- Treatment did not change between the onset of the occurrences OR treatment changed between the onset of the occurrences, but no deterioration was observed for the later occurrence

For further details on summarization of AE data, please refer ([3](#), [4](#))

AE analyses will be carried out after integrating AE data from CRF and AE data from perceive system.

In addition, AEs coded as “no adverse event” will not be included in the AE analyses.

The analysis of adverse events will be based on the concept of treatment emergent adverse events. That means that all adverse events occurring between first drug intake till 30 days after last drug intake will be analysed. For details on the treatment definition, see [Section 6.1](#).

An overall summary of adverse events will be presented.

The frequency of patients with AEs, ADRs will be summarised by primary system organ class and preferred term. Also, the frequency of patients with ADRs will be summarised by primary system organ class, preferred term and the time to first onset date (1 to 30, 31 to 60, 61 to 90, 91 to 180, 181 to 365, >=366 days). Separate tables will be provided for patients with ADRs stratified by various patient subgroups defined in [Section 6.4](#), for patients with serious AEs. Subgroup analysis will display the frequency of patients, percentage (%) and odds ratio with 95%CI. Logistic regression will be used for odds ratio. The ‘unknown’ and ‘missing’ categories are excluded to calculate odds ratio. Patients with ‘priority survey items’ according to the drug’s Risk Management Plan will be summarised separately.

An ADR is defined as an AE for which either the investigator or the sponsor (or both) assess the causal relationship to Spiriva Respimat either as “Possibility high”, “Possibility low” or “Unknown”. The system organ classes will be sorted according to the standard sort order specified by EMA, preferred terms will be sorted by frequency (within system organ class).

A serious AE is defined as an AE for which either the investigator or the sponsor (or both) assess the seriousness either as “Serious”.

The following AEs are detected on the basis of the Standardised MedDRA queries (SMQs) or Boehringer Ingelheim customised MedDRA query (BICMQ) (details are described in ADS plan).

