4. ABSTRACT

Name of company: Boehringer Ingelheim			
Name of finished medicinal product: SPIRIVA Respimat			
Name of active ingredient: Tiotropium bromide			
Protocol date: 15 April 2015	Study number: 205.525	Version/Revision: Ver 1.0	Version/Revision date: n.a.
Title of study:	Specific Use-Result Surveillance of Spiriva Respimat in asthmatics (patients with severe persistent asthma)		
Rationale and background:	The safety of Spiriva® 2.5 µg Respimat® 60 puffs (hereinafter referred to as Spiriva® Respimat®) in patients with severe persistent asthma under the real-world use was not confirmed in clinical trials.		
Research question and objectives:	This PMS is designed; To investigate the safety and effectiveness of Spiriva Respimat in patients with severe persistent asthma under real-world use.		
Study design:	Non-interventional, observational study based on new data collection		
Population:	Inclusion criteria: 
• Patients diagnosed with severe persistent bronchial asthma• Patient aged ≥ 15 years old• Patients who are naive to Spiriva respimat and receive Spiriva Respimat for the first time for the treatment of bronchial asthma on top of at least ICS treatment.		
Variables:	Demographics Medical history/baseline conditions Previous/concomitant therapies Pulmonary function test (peak expiratory flow rate, forced expiratory volume in 1 second, forced vital capacity), if available Asthma severity and asthma control status, if available ACQ 6 score, if available Spiriva Respimat administration Adverse event Safety laboratory test (if corresponding AEs are reported)		
Data sources:	Patients data will be gathered by electronic Case Report Form on EDC		
Study size:	300 (safety set)		
Data analysis:	Descriptive		
Milestones:	Final report will be made by 1 Apr 2018 Study result in re-examination will be submitted to PMDA (Jan. 2019)		

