9.2.3 Observations

After start of the treatment with Spiriva Respimat, each patient will be observed for 52 weeks (approximately 12 months) or at premature discontinuation from the PMS. Observations are made at the following time points: before first administration of Spiriva Respimat (this visit is defined as baseline), 4 weeks, 12 weeks and 52 weeks after the start of treatment, or at discontinuation.

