## **7. PLANNED ANALYSIS**

For End-Of-Text (EoT) tables, the set of summary statistics is: N / Mean / SD / Min / Q1 / Median / Q3 / Max.

For tables that are provided for endpoints with some extreme data, median, quartiles and percentiles should be preferred to mean, standard deviation, minimum and maximum.

Tabulations of frequencies for categorical data will include all possible categories and will display the number of observations in a category as well as the percentage (%) relative to the respective treatment group (unless otherwise specified, all patients in the respective patient set whether they have non-missing values or not). Percentages will be rounded to one decimal place. The category missing will be displayed only if there are actually missing values.

In addition, individual values on demographics, safety and effectiveness will be presented in subject data listings.

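### The ADR time-to-onset table uses intervals of very unequal length with no number at risk or patient-time, so a fall in risk after the first three months can be masked.

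*SAP*

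**What the plan says.** SAP 7.8.1 counts patients with ADRs within each MedDRA class and term, broken down as follows: "the time to first onset date (1 to 30, 31 to 60, 61 to 90, 91 to 180, 181 to 365, >=366 days". The unit is the patient: "All analyses of AEs will be based on the number of patients with AEs and NOT on the number of AEs".

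SAP 7.8 sets the population: "All safety analyses will be performed on the safety set". The Protocol abstract plans this set at "300 (safety set"). SAP 7 sets the default base for percentages as "all patients in the respective patient set whether they have non-missing values or not". SAP 7.8.1 makes no exception for the onset table. Exposure is summarised separately and only descriptively (SAP 7.7).

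On follow-up, Protocol 9.2.3 states that "each patient will be observed for 52 weeks (approximately 12 months) or at premature discontinuation from the PMS". ADR collection runs longer: Protocol 11.2 requires it until 30 days after last intake, and Protocol 9.7.2 and SAP 7.8.1 analyse the same window. SAP 7.8.1 also draws on a second source: "AE analyses will be carried out after integrating AE data from CRF and AE data from perceive system".

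**The concern.** An onset table is read to see when reactions occur. The fifth interval is 185 days long and the first three are 30 days each, so it collects more patients simply because it is longer. Without the number at risk or patient-time, a reader cannot separate interval length, attrition and any real change in risk.

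Two misreadings follow. A constant risk can look like a late accumulation of ADRs. A risk that falls after the first three months can look flat or even rising.

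The open interval has a related difficulty. It depends on a subset of patients whose size is not shown, and the documents do not say when counting stops for patients who remain on treatment after week 52.

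**Working it through.** **Figures in the plan.** Protocol 9.5: 360 enrolled - 60 lost without data = 300, which matches the planned safety set. Protocol 9.2.3: 52 × 7 = 364 days. The plan gives no expected count or rate for the onset table.

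**Interval lengths.** Days 1-30, 31-60 and 61-90 are 30 days each, days 91-180 are 90 and days 181-365 are 185. If last intake is on day 364, collection runs to 364 + 30 = 394, so days 366-394 add 29.

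**Assumptions.** The overall ADR risk and the discontinuation rate are not in the documents. I used 52-week risks p of 1.8% (the per-term figure for the Japanese asthma trial in Protocol 9.5), 5%, 10% and 20%, and discontinuation q by day 364 of 0 to 70%.

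**Model.** The daily hazard is constant, h = -ln(1 - p)/364, and discontinuation is exponential, g = -ln(1 - q)/364. A patient stays at risk until 30 days after last intake. Patient-days on day d = 300 × exp(-g × max(0, d - 31)) × exp(-h × (d - 1)). Expected first onsets on day d = patient-days × (1 - exp(-h)). Both are summed within each interval.

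**Constant 10% risk, no discontinuation** (h = 0.10536/364 = 0.000289 per day):

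| Days | Patients | % of 300 | Rate per 100 patient-years |
|---|---|---|---|
| 1-30 | 2.59 | 0.86 | 10.57 |
| 31-60 | 2.57 | 0.86 | 10.57 |
| 61-90 | 2.55 | 0.85 | 10.57 |
| 91-180 | 7.52 | 2.51 | 10.57 |
| 181-365 | 14.85 | 4.95 | 10.57 |
| 366-394 | 2.26 | 0.75 | 10.57 |

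The ratio of days 181-365 to days 1-30 is 14.85/2.59 = 5.7.

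**Same risk, 40% discontinuation:**

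| Days | Patients | % of 300 | At risk at start | Patient-days | Rate per 100 patient-years |
|---|---|---|---|---|---|
| 1-30 | 2.59 | 0.86 | 300.0 | 8,962 | 10.57 |
| 31-60 | 2.52 | 0.84 | 297.4 | 8,707 | 10.57 |
| 61-90 | 2.40 | 0.80 | 282.7 | 8,276 | 10.57 |
| 91-180 | 6.50 | 2.17 | 268.7 | 22,448 | 10.57 |
| 181-365 | 10.61 | 3.54 | 230.7 | 36,676 | 10.57 |
| 366-394 | 1.38 | 0.46 | 168.7 | 4,778 | 10.57 |

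The ratio is 10.61/2.59 = 4.1. The late percentage is lower than without attrition (3.54 against 4.95), so the fixed base works against the apparent rise.

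**Range of the ratio.** It is highest at 1.8% risk with no discontinuation (6.1) and lowest at 20% risk with 70% discontinuation (13.22/5.47 = 2.4). Dividing by patient-time gives a flat rate in every scenario.

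**How much decline can be masked.** On lengths alone, the daily risk in days 181-365 could be 30/185 = 16% of the first month's and the two counts would be equal. For days 91-180 the figure is 30/90 = 33%.

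**Last interval.** To be at risk on day 366, a patient needs a last intake on about day 336 or later (366 - 30). Across the scenarios this interval holds 3.3 to 7.3% of first onsets.

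**The case against.** The table is descriptive, carries no test or decision rule, and shows its interval bounds, so a careful reader can allow for length. That is a fair argument for low priority. It does not let the reader recover the number at risk or the patient-time, which are not planned anywhere for this table. SAP 7.8.1 defers some AE summarisation detail to references that are not in the public documents, so the final layout cannot be judged completely.

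Four stronger readings are tempting, and the documents do not support them.

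- **The fixed denominator creates the late rise.** It does the opposite: attrition over a fixed base lowers late percentages. Interval length alone produces the rise.
- **An excess in the first month is hidden.** The first three intervals are equal, so an excess over months two and three is directly visible. What can be masked is a decline after that.
- **The interval from day 366 lies outside follow-up.** It lies beyond the 52-week observation, but not beyond the 30-day window after last intake that Protocol 9.7.2 and 11.2 require. Visit times are also approximate (Protocol Annex 3).
- **Counting should stop at 52 weeks.** That would discard ADRs that the Protocol defines as treatment-emergent: those in the last interval, 3.3 to 7.3% of modelled first onsets, and any on day 365.

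It is also true that rates by preferred term would be unstable. At 1.8% risk, each of the first three intervals expects only 0.45 patients.

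**Conclusion.** The point holds as a matter of presentation and interpretation for one descriptive table. Under constant risk, the planned layout puts 2.4 to 6.1 times as many patients in days 181-365 as in days 1-30, so a substantial decline after month three could go unnoticed. The size rests on a constant hazard, exponential discontinuation and assumed ranges for both rates. The direction rests only on the interval lengths and holds at every value tried.

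A separate gap is that the window has no stated end for patients still on treatment after week 52. Registration runs from June 2015 to May 2016 and data collection ends on 31 August 2017 (Protocol 6 and 9.2.2.3). The possible calendar span is therefore about 822 days from 1 June 2015 and about 457 days from 31 May 2016. Reports merged from the second safety source could reach the open interval with unequal opportunity across patients.

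A reader might infer that the primary outcome, the frequency of patients with ADRs, is distorted. The table layout does not change it. Priority: optional to low.

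**What to change.** In SAP 7.8.1:

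1. Keep the patient counts and the existing intervals.
2. For each interval, add the number at risk at its start, the patient-time and the first-onset rate per 100 patient-years. Do this for any ADR overall and, where counts allow, by system organ class or preferred term. At risk means under observation with no earlier onset of that same category.
3. Keep the Protocol's window of last intake plus 30 days, with no cut at 52 weeks.
4. State when counted observation ends for patients who continue treatment after week 52, and list reports after that point separately.

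The cost is SAP wording and a few more table columns. First and last intake dates and interruptions already feed the exposure duration in SAP 5.4, so no new data are needed. Many preferred-term rates will be sparse, so the overall rows will be the most useful.
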